#### 9.5.1.2 Sensitivity Analysis of Primary Estimands

Sensitivity analysis will be carried out using Multiple Imputation (MI) for handling missing IGA or EASI that prevents the primary endpoints being derived. The imputation model for IGA score will include treatment group, age and IGA values at all

available time points up to week 16 as covariates. The imputed IGA scores will be used to derive IGA 0/1 at week 16 per [Section 5.5](#). Similarly, the imputation model for EASI score will include treatment group, age and EASI values at all available time points up to week 16 as covariates. The imputed scores will then be used to derive EASI 75 at week 16 per [Section 5.5](#).

As a second sensitivity analysis, LOCF imputation will be used for handling missing data that prevents the primary endpoints being derived. The treatment effect for IGA 0/1 at week 16 will be analyzed using a logistic regression model, with baseline IGA scores and age as covariates. Similarly, the treatment effect for EASI 75 at week 16 will be analyzed using a logistic regression model with baseline EASI scores and age as covariates.

Third sensitivity analysis will use the same logistic regression models used in [Section 9.5.1.1](#) with an additional covariate, screening total serum IgE level (< 150 kU/L or  $\geq$  150 kU/L).

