## **4. Covariates and Subgroups**

### **4.1 Planned Covariates**

The analysis of the primary endpoints will be adjusted for the baseline covariate as follows:

- **Primary endpoint – IGA 0/1 at week 16:** Baseline IGA
- **Primary endpoint – EASI 75 at week 16:** Baseline EASI

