### **9.5.1 Analyses of Primary Efficacy Endpoint(s)**

#### **9.5.1.1 Primary Analysis of the Primary Endpoints**

[figure not shown]
The primary analysis of the primary estimands as defined in [Section 2.1](#) will be performed using the FAS – Part A. Primary endpoints are defined in [Section 5.5](#). **Where an endpoint cannot be derived due to missing IGA or EASI assessments, a patient will be assumed not to have achieved the outcome, that is, Non-Responder Imputation (NRI).**

Treatment effect **for IGA 0/1 at week 16** will be tested using a logistic regression model with baseline IGA as covariate. **Similarly, treatment effect for EASI 75 at week 16 will**

**be tested using a logistic regression model with baseline EASI as covariate.** From **each** model, odds ratio and 95% CIs will be reported, comparing each tezepelumab dose group to placebo.

To control the family-wise type 1 error rate at 0.05 (**2-sided**) for the multiple comparisons of 420 mg vs. placebo and 280 mg vs. placebo, the hypotheses **described in Section 2.2** will be tested using a Bonferroni-based gatekeeping chain procedure (**Dmitrienko 2013**) as shown in [Figure 9-1](#). This procedure will split alpha of 0.05 equally to test in parallel tezepelumab 420 mg SC Q2W versus placebo and tezepelumab 280 mg SC Q2W versus placebo for IGA 0/1 and EASI 75 sequentially within each parallel **dose** path. If one of the parallel **dose** paths rejects **the 2** hypotheses sequentially, and the other **dose** path has at least one hypothesis not rejected, then the unspent  $\alpha$  of 0.025 from the successful path will be propagated to the **unsuccessful dose path** to retest the 2 hypotheses sequentially at a level of 0.05.

Figure 9-1. Alpha Split Between Two Doses of Interest

In addition, analysis of primary endpoints may be considered using mFAS-Part A as a supporting analysis to examine the impact of COVID-19 2020 outbreak on outcomes without multiplicity adjustment.

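### The LOCF sensitivity analysis also adds age to the model, so a difference from the primary odds ratio is not cleanly attributable to the missing-data method

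*SAP*

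**What the plan says.** SAP 4.1 fixes one baseline covariate per primary endpoint: "The analysis of the primary endpoints will be adjusted for the baseline covariate as follows", followed by baseline IGA for IGA 0/1 and baseline EASI for EASI 75. Protocol 10.2.2 lists the same two.

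SAP 9.5.1.1 carries this into the primary analysis. A missing outcome counts as non-response (NRI). The treatment effect on IGA 0/1 "will be tested using a logistic regression model with baseline IGA as covariate", and the effect on EASI 75 will "be tested using a logistic regression model with baseline EASI as covariate".

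SAP 9.5.1.2 then lists three sensitivity analyses:

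- **First:** multiple imputation (MI). Age appears in the imputation model. The outcome model fitted afterwards is not named.
- **Second:** "LOCF imputation will be used for handling missing data that prevents the primary endpoints being derived". IGA 0/1 is then analysed "using a logistic regression model, with baseline IGA scores and age as covariates", and EASI 75 "using a logistic regression model with baseline EASI scores and age as covariates".
- **Third:** the 9.5.1.1 models with screening IgE category as one extra covariate.

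SAP 9.5 makes all sensitivity analyses descriptive, with nominal p-values and no multiplicity adjustment. No reason is given for age in the LOCF model.

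**The concern.** A missing-data sensitivity analysis is read by setting its estimate beside the primary one and asking what the change of missing-data rule did. That reading needs everything else to be held fixed. Here the outcome model changes too, for both primary endpoints.

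The summary measure in SAP 2.1 is an odds ratio. Adding a prognostic covariate to a logistic model moves the treatment odds ratio even when the arms are perfectly balanced (non-collapsibility). With about 60 per arm, adjusting for chance age imbalance moves it further. A gap between the LOCF and primary results would then mix two sources. Close agreement could, in principle, reflect two shifts that offset each other.

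Age does nothing for the missing data in this analysis. In MI it can help to predict missing scores, but LOCF has no imputation model.

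**Working it through.** **1. The analyses side by side.** The plan states no figure on this point, so the core of the check is textual.

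| Analysis | Missing-data rule | Covariates in outcome model | Features changed from primary |
|---|---|---|---|
| Primary (9.5.1.1) | NRI | baseline score | – |
| Sensitivity 1 (9.5.1.2) | MI | not stated; age named only for imputation | rule |
| Sensitivity 2 (9.5.1.2) | LOCF | baseline score + age | rule and model |
| Sensitivity 3 (9.5.1.2) | NRI | baseline score + IgE category | model |

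There is no NRI analysis with age and no LOCF analysis without it, so the two changes in sensitivity 2 cannot be separated from planned output. Sensitivity 3 shows that the SAP elsewhere changes one feature at a time.

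**2. Why age alone moves the estimate.** SAP 3.2 assumes IGA 0/1 rates of 10% and 40%, an odds ratio of (0.40/0.60)/(0.10/0.90) = 6.0. As an illustration, take two equal age halves, perfectly balanced across arms, with placebo rates of 15% and 5% (mean 10%) and an odds ratio of 6 within each half:

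- Treated odds: 6 × 0.15/0.85 = 1.059 (rate 51.4%) and 6 × 0.05/0.95 = 0.316 (rate 24.0%); mean rate 37.7%.
- Odds ratio ignoring age: (0.377/0.623)/(0.10/0.90) = 5.45.
- Shift from adjusting for age: ln(6/5.45) ≈ 0.10, with no imbalance at all.

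The age effect in this example is ln(0.176/0.0526) = 1.21 between halves. The SD of a half-and-half split is 0.5, so this is about 0.6 log-odds per SD.

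**3. Size by simulation.** Inputs from SAP 3.2: 60 per arm, 10% versus 40% for IGA 0/1, 15% versus 50% for EASI 75, and 10% dropout used as the missing share. The strength of the age effect and the carry-forward behaviour are assumptions. In each trial,

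- LOCF shift = log OR(LOCF, baseline) − log OR(NRI, baseline);
- age shift = log OR(LOCF, baseline + age) − log OR(LOCF, baseline).

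*Set-up A* (IGA 0/1; about 2,900–3,000 trials per setting; baseline slope −0.4 per SD; LOCF from a correlated week-12 status). The median absolute LOCF shift is 0.13–0.14. The median absolute age shift runs from 0.02 (no age effect) to 0.11 (0.6 log-odds per SD).

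| Age effect, log-odds per SD | 0 | 0.2 | 0.4 | 0.6 |
|---|---|---|---|---|
| Trials with age shift larger than LOCF shift | 16% | 21% | 32% | 47% |

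*Set-up B* (about 2,000 trials per setting; two-level baseline severity, log OR −0.7; 60% of missing would-be responders carried forward as responders). LOCF alone multiplies the odds ratio by a median of about 1.07. For age alone:

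| Age OR per SD | IGA 0/1: median factor (95% range) | EASI 75: median factor (95% range) | Age shift at least as large as LOCF shift (IGA 0/1, EASI 75) |
|---|---|---|---|
| 1.0 | 1.01 (0.93–1.19) | 1.01 (0.94–1.18) | 23%, 18% |
| 1.5 | 1.04 (0.91–1.52) | 1.05 (0.92–1.45) | 40%, 39% |
| 2.0 | 1.13 (0.91–1.92) | 1.15 (0.91–1.85) | 60%, 60% |

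Since ln 1.5 = 0.41 and ln 2.0 = 0.69, the last row lies beyond the range of set-up A. The set-ups agree in direction and rough size.

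**4. Size against sampling error.** The standard error of the IGA 0/1 log odds ratio is about 0.54. The median age shift is therefore 0.02/0.54 ≈ 4% to 0.11/0.54 ≈ 20% of one standard error. In set-up B, adding age under NRI changed significance at 0.025 in about 1–3% of trials.

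**The case against.** The strongest reply concerns consequence, and most of it stands.

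- **LOCF is not the only missing-data check.** MI comes first in 9.5.1.2, and nothing in its text puts age in the outcome model. A reader might infer that the robustness of the primary result to missing data goes untested. The documents do not support that.
- **Nothing confirmatory depends on it.** SAP 9.5 makes the analysis descriptive. A reader might infer that the primary test or the type I error is compromised, but both rest on 9.5.1.1, which is unchanged.
- **It breaks no rule.** Protocol 10.2.2 allows further covariates in exploratory analyses, and Protocol 10.2.4 says only that LOCF may be considered. Age is prespecified, so it adds no data-driven choice.
- **Imputation is usually the larger contributor.** In set-up A the age shift is not the larger one in 84%, 79%, 68% and 53% of trials. This fails only for a stronger age effect: at an odds ratio of 2.0 per SD, age is at least as large in about 60%.
- **When age dominates, there is often little to explain.** In a further run of about 2,490 trials per setting (60% of missing responders and 5% of missing non-responders carried forward as responders), the age shift was larger in 18%, 23%, 34% and 47%. In 91%, 90%, 78% and 67% of those trials the LOCF shift was below 0.10 log-odds. Material cancellation, meaning an opposite age shift at least half the size of a LOCF shift above 0.10, occurred in 2–12%. Nominal significance at 0.05 changed in 0.2–1.5%.

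These points limit the weight of the matter. None of them removes the double change. The sponsor could add an LOCF run without age at analysis, but prespecification exists to make that unnecessary.

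**Conclusion.** The point holds in a narrow form. The LOCF analysis changes the missing-data rule and the covariate set together, for IGA 0/1 and EASI 75, so its difference from the primary odds ratio is not cleanly attributable to LOCF. To say that such a difference can never be attributed, or that the missing-data question goes unanswered, would claim more than the documents and the numbers bear.

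The size rests on an age effect that neither document gives. Over the assumed range of 0 to 0.6 log-odds per SD, the median age shift is about 0.02 to 0.11 log-odds, against 0.13–0.14 for LOCF. It is negligible if age is unrelated to response and comparable with the LOCF shift at the upper end. The comparison also assumes 10% missing outcomes. With fewer, the LOCF shift would shrink while the age shift would largely remain. This is an improvement to interpretability and does not threaten the trial's conclusions.

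**What to change.** In SAP 9.5.1.2, delete the words *and age* from the IGA 0/1 and EASI 75 sentences of the LOCF analysis, so that LOCF uses the 9.5.1.1 models unchanged. If age adjustment is of interest, specify it as its own covariate analysis under NRI, alongside the IgE analysis.

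The cost is two small deletions in the SAP, with no effect on data collection, sample size or conduct. As a separate clarification in the same edit, one sentence could name the outcome model fitted after MI, which the SAP leaves unstated.

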#### 9.5.1.3 Subgroup Analyses of Primary Endpoints

The consistency of the detected overall treatment effect on the primary endpoints will be explored for Part A only. A logistic regression model will include baseline IGA or EASI, the subgroup being tested, treatment, and treatment by subgroup interaction. The odds ratio will be calculated for each category of subgroup populations. The subgroups mentioned in [Section 4.2](#), will be used in this subgroup analyses.

#### 9.5.2 Analyses of Secondary Efficacy Endpoint(s)

The secondary estimands will be analyzed using **FAS – Part A**. Secondary endpoints are defined in [Section 5.6](#).

For the binary endpoint, EASI 50/90 at week 16, the treatment effect will be **analyzed** using a logistic regression model adjusting for baseline EASI. From this model, odds ratio and 95% CIs will be reported comparing each tezepelumab dose group to placebo.

The time to achieving EASI 50/75/90 response prior to switching to tezepelumab 420 mg Q2W will be summarized by Kaplan-Meier (KM) curves, the number of subjects achieving EASI 50/75/90 and the number of subjects censored will be provided at available time points. Subjects who do not achieve EASI 50/75/90 will be censored at the date when formal assessments of non-responder (as defined in protocol, that is, not achieve at least 50% improvement in EASI at week 16

compared to baseline) are recorded or end of study date, whichever is the earliest. Subjects who receive rescue medication from day 29 will be censored at the point when subjects receive rescue medication.

The treatment effect for change from baseline in SCORAD and Pruritus NRS each at week 16 will be analyzed using a **Mixed Model for Repeated Measures (MMRM)**. The model for change from baseline in SCORAD at week 16 will include visit and baseline SCORAD as covariates and an interaction term between arm and visit. The model for change from baseline in Pruritus NRS at week 16 will include visit and baseline Pruritus NRS as covariates and an interaction term between arm and visit. **AR(1) variance-covariance structure will be used.** Least square means and corresponding 95% CI will be calculated for each treatment group and for the difference between treatment groups.

Serum concentration will be summarized descriptively by treatment group for each sampling time point using the PK analysis set.

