## 2. Objectives, Endpoints and Hypotheses

### 2.1 Objectives and Endpoints

Objectives	Endpoints
Primary – Part A	

To evaluate the effect of tezepelumab compared with placebo, assessed using the Investigator's Global Assessment (IGA) and Eczema Area and Severity Index (EASI)

	

IGA score of 0 (clear) or 1 (almost clear) (IGA 0/1) at week 16

75% reduction in EASI (EASI 75) at week 16

The first primary estimand consists of:

- Target population – patients with moderate-to-severe atopic dermatitis (**AD**).
- Endpoint – IGA 0/1 at week 16.
- Intercurrent event – there are 2 intercurrent events, discontinuation of IP before week 16 and **concurrent use** of rescue medication **with TCS/TCI** between day **29** and week 16. Treatment effects will be estimated for subjects regardless of whether patients complete 16 weeks of **study treatment**. The use of rescue medication is captured through the endpoint definition in **Section 5.5, and use of TCS/TCI will be classed as a non-response**.
- Summary measure – odds ratio comparing the odds of achieving endpoint on tezepelumab 420 mg Q2W compared to the odds of achieving endpoint on placebo.

In summary, the first primary estimand is the odds ratio between tezepelumab 420 mg Q2W and placebo in achieving IGA 0/1 at week 16, in the absence of rescue medication with **TCS/TCI regardless of whether patients complete 16 weeks of study treatment**, in patients with moderate-to-severe AD.

The second primary estimand is the odds ratio between tezepelumab 280 mg Q2W and placebo in achieving IGA 0/1 at week 16, in the absence of rescue medication with **TCS/TCI regardless of whether patients complete 16 weeks of study treatment**, in patients with moderate-to-severe AD.

The third primary estimand is the odds ratio between tezepelumab 420 mg Q2W and placebo in achieving EASI 75 at week 16, in the absence of rescue medication with **TCS/TCI regardless of whether patients complete 16 weeks of study treatment**, in patients with moderate-to-severe AD.

The fourth primary estimand is the odds ratio between tezepelumab 280 mg Q2W and placebo in achieving EASI 75 at week 16, in the absence of rescue medication with **TCS/TCI regardless of whether patients complete 16 weeks of study treatment**, in patients with moderate-to-severe AD.

Secondary – Part A	

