

To estimate the effect of tezepelumab compared with placebo on the efficacy measure of EASI

	

50% and 90% reduction in EASI (EASI 50/90) at week 16

To estimate the time needed to reach EASI 50/75/90

	

Time at which EASI 50/75/90 is achieved from day 1

To estimate the effect of tezepelumab compared with placebo on the efficacy measure of Scoring Atopic Dermatitis (SCORAD)

	

SCORAD at week 16

To estimate the effect of tezepelumab compared with placebo on the patient-reported outcome (PRO) measure of pruritus assessed using a numeric rating scale (NRS)

	

Pruritus NRS at week 16

To characterize the pharmacokinetics (PK) of tezepelumab

	

Serum trough concentrations of tezepelumab at scheduled visits

The secondary estimands are described in the same way as primary estimands except the endpoint attribute will change for EASI 50/90 at week 16, SCORAD at week 16 and Pruritus NRS at week 16, where the summary measure changes to be the Least Square Mean difference; and time at which EASI 50/75/90 is achieved from day 1, where the summary measure changes to be the median time to achieve EASI 50/75/90 from day 1.

Safety – Part A and Part B	

 
To establish the safety and tolerability of tezepelumab compared with placebo
 
	
 
Subject incidence of adverse events (including serious adverse events)
 

Exploratory – Part A and Part B	

 
To estimate the long-term effect of tezepelumab on the efficacy measures of EASI, SCORAD, and Pruritus NRS
 
	
 
IGA 0/1 at week 24, week 36, and week 52
 
EASI 75 at week 24, week 36, and week 52
 
EASI 50/90 at week 24, week 36, and week 52
 
SCORAD at week 24, week 36, and week 52
 
Pruritus NRS at week 24, week 36, and week 52
 

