### Eczema Area and Severity Index (EASI)

The EASI is designed by modifying the Psoriasis Area and Severity Index, which has been widely used in clinical trials and has been established as a well-accepted and standardized instrument for assessing therapeutic response in patients with psoriasis ([Schmitt et al, 2007](#)). The EASI evaluates 4 natural anatomical regions for severity and extent of key disease signs and focuses on key acute and chronic signs of inflammation (ie, erythema, induration/papulation, excoriation, and lichenification). The maximum score is 72, with higher values indicating more severe disease.

For subjects who take rescue medication of TCS/TCI from day 29, their EASI score will be ignored on and after the date of rescue medication.

Body Region	Severity	Area	Score
Head/Neck (H)	The average degree of severity of each sign (erythema [E], induration/papulation [I], excoriation [EX] and lichenification [L], is defined on a 4-point ordinal scale:  0 = none 1 = mild 2 = moderate 3 = severe	The area is defined on a 7-point ordinal scale:  0 = no eruption 1 = <10% 2 = 10% - 29% 3 = 30% - 49% 4 = 50% - 69% 5 = 70% - 89% 6 = 90% - 100%	$(E+I+EX+L) * Area * 0.1$
Upper Limbs (UL)			$(E+I+EX+L) * Area * 0.2$
Trunk (T)			$(E+I+EX+L) * Area * 0.3$
Lower Limbs (LL)			$(E+I+EX+L) * Area * 0.4$
EASI Score			Sum of scores of H, UL, T, and LL

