## 5.6 Secondary/Exploratory Endpoints – IGA 0/1 and EASI 50/75/90

Secondary endpoints, EASI 50 and EASI 90 at week 16 in Part A, and Exploratory endpoints, IGA 0/1 at week 24, week 36 and week 52 in Part A and B, and IGA 0/1 at week 16 in Part B, will be defined in the same way as primary endpoints in [Section 5.5](#). For example, the time point of interest is week 24, week 36 and week 52 instead of week 16, the use of TCS/TCI will be considered from day 29, to week 24, week 36 and week 52 respectively.

Time-to-event analysis of EASI 50/75/90 will be handled as described in [Section 9.5.2](#) and [Section 9.5.3](#).

In addition, IGA 0/1 and EASI 75 at time points other than week 16, week 24, week 36 and week 52 in both Part A and B will be defined in the same way as primary endpoints in [Section 5.5](#) at corresponding time points. For example, when the time point of interest is week 4, week 6, week 8, week 10, and week 12 instead of week 16, the use of TCS/TCI will be considered from day 29, to those time points respectively.

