#### *Part B*

The analysis of exploratory endpoints for Part B will be performed using the **FAS – Part B**. The methods of analyses of exploratory endpoints for Part B will be the same as the analysis of exploratory endpoints for Part A. In addition, Bayesian methods may be used to borrow historical control data in estimating treatment effect, in addition to using observed data from the current study.

The time to achieving EASI 50/75/90 response prior to switching to tezepelumab 420 mg Q2W will be summarized by Kaplan-Meier (KM) curves, the number of subjects achieving EASI 50/75/90 and the number of subjects censored will be provided at available time points. Subjects who do not achieve EASI 50/75/90 will be censored at the date when formal assessments of non-responder (as defined in protocol, that is, not achieve at least 50% improvement in EASI at week 16 compared to baseline) are recorded or end of study date, whichever is the earliest. Subjects who receive rescue medication from day 29 will be censored at the point when subjects receive rescue medication.

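### Time to EASI 50/75/90: SAP 9.5.2 censors at rescue although SAP 2.1 counts rescue as non-response, and the Part B text repeats Part A rules that do not fit Part B

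*SAP*

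**What the plan says.** **Estimand.** In SAP 2.1 the primary estimand handles rescue through the endpoint definition: "use of TCS/TCI will be classed as a non-response". For the secondary endpoints, "The secondary estimands are described in the same way as primary estimands except the endpoint attribute will change". Time to EASI 50/75/90 is named there, and for it "the summary measure changes to be the median time to achieve EASI 50/75/90 from day 1".

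**Scores after rescue.** In SAP 5.4, for subjects who take TCS/TCI rescue from day 29, "their EASI score will be ignored on and after the date of rescue medication". SAP 5.5 codes such a subject as 0 for the binary endpoint, and SAP 5.6 applies the same derivation to EASI 50 and EASI 90 at week 16.

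**Time-to-event analysis.** SAP 5.6 says only this: "Time-to-event analysis of EASI 50/75/90 will be handled as described in" 9.5.2 and 9.5.3. It defines no other estimand. SAP 9.5.2 has two censoring rules. One is for rescue: "Subjects who receive rescue medication from day 29 will be censored at the point when subjects receive rescue medication". The other is for failure: "Subjects who do not achieve EASI 50/75/90 will be censored at the date when formal assessments of non-responder" are recorded, meaning an EASI-50 failure at week 16, or at end of study if that is earlier.

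**Part B.** SAP 9.5.3.1 repeats the paragraph: "The time to achieving EASI 50/75/90 response prior to switching to tezepelumab 420 mg Q2W will be summarized by Kaplan-Meier (KM) curves", with the same two censoring rules. SAP 3.1 and protocol 7.4 state that nobody in Part B is switched. Protocol 7.1.5 bars rescue in the first 4 weeks of Part A. In Part B it permits TCS once day 1 activities are done, and rescue after the week 2 visit. Protocol 7.1.7 agrees on Part B.

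**The concern.** Censoring at rescue treats a rescued subject as someone who, had follow-up continued, would have gone on to respond at the same rate as those still at risk. The estimand says the opposite: that subject has failed. Within 9.5.2 the same rescued subject is therefore a failure in the week-16 EASI 50/90 logistic model and a censored observation in the Kaplan-Meier curve. Rescue is given for intolerable symptoms, so it is unlikely to be unrelated to prognosis.

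At stake are the plotted curve and the median, which is the stated summary of a secondary endpoint. They would not agree with the response rates reported beside them. In Part B, the copied text can drop usable data on unchanged treatment and leaves open what counts as rescue.

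**Working it through.** **1. Reference figures.** The documents give no figure for the Kaplan-Meier analysis and no rescue rate. The nearest stated values are the EASI 75 design rates at week 16, 15% on placebo and 50% on 420 mg Q2W (protocol 10.1, SAP 3.2). Their odds ratio is (0.50/0.50)/(0.15/0.85) = 5.67, as in SAP 5.4. I use these rates as illustrative shares achieving *by* week 16. The share by week 16 cannot be lower than the share at week 16 under the same rules.

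**2. Direction.** Let f_k be the share first achieving at visit k, and R_k the share rescued without achieving before visit k.
- Rescue as non-response: conditional probability f_k / (1 - earlier f).
- Rescue censored: f_k / (1 - earlier f - R_k).

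The second denominator is never larger, so 1-KM is never below the cumulative response in that arm. It is above it as soon as one subject responds after another has been rescued. The median can only be the same or earlier.

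**3. Size at week 16.** EASI visits are weeks 4, 6, 8, 10, 12 and 16 (protocol Table 2-1). F is the share achieving by week 16. The share rescued, rho, is assumed and spread uniformly over weeks 4-16, so R_k = rho(t_k - 4)/12. Then 1-KM(16) = 1 - product of [1 - f_k/(1 - earlier f - R_k)].

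Worked case, F = 0.50 in equal steps of 0.0833, rho = 0.10:

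| Week | At risk | Factor |
|---|---|---|
| 4 | 1.0000 | 0.9167 |
| 6 | 0.9000 | 0.9074 |
| 8 | 0.8000 | 0.8958 |
| 10 | 0.7000 | 0.8810 |
| 12 | 0.6000 | 0.8611 |
| 16 | 0.4833 | 0.8276 |

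The product is 0.468, so 1-KM = 53.2%. With rho = 0 the formula returns 50.0%, as it should.

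Four timing patterns (equal per visit; proportional to the interval; weights 1 to 6; weights .02/.04/.08/.14/.24/.48) give:

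| F | Rescued | 1-KM at week 16 |
|---|---|---|
| 50% | 10% | 53.2, 53.4, 54.0, 54.7% |
| 50% | 20% | 57.4, 58.0, 59.2, 60.7% |
| 15% | 10% | 15.8, 15.8, 16.0, 16.3% |
| 15% | 40% | 19.2, 19.7, 20.8, 22.3% |

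**4. Median.** Solving 1-KM(16) = 50% for F: with 10% rescued, a median appears by week 16 once F is 45.8-47.0%; with 20% rescued, once F is 41.5-43.9%.

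**5. Between arms.** With equal rescue of 10%, the odds ratio computed from 1-KM is 6.1-6.2, against 5.67. With 40% rescued on placebo and 20% on 420 mg it is 5.4-5.7, while the difference is about 38 points (57.4 - 19.2; 60.7 - 22.3) against 35. The direction depends on the rescue pattern and on the measure.

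**6. Part B.** No arithmetic applies.
- *Switch and week-16 censoring.* There is no switch, so that qualifier has no effect. SAP 5.2 ties the eCRF non-responder determination to Part A, so it is unclear whether a Part B censoring date will exist. If it does, EASI after week 16 on unchanged treatment is dropped. If it does not, follow-up runs to end of study.
- *Day 29.* The start day fits Part A's 4-week bar. Part B rescue may begin after week 2, roughly day 15, and 9.5.3.1 does not say which TCS use is rescue and which is permitted background. SAP 5.6 carries the same day-29 rule for TCS/TCI use to the Part B binary endpoints.

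**The case against.** **The estimand can be read differently.** SAP 2.1 also describes response in the absence of rescue, which could be taken as hypothetical and would suit censoring. The non-response coding in 5.5 is written for binary endpoints, and the sentence in 2.1 that carries it forward also covers SCORAD and Pruritus NRS, which have no responder status. This has some force: the overstatement is measured against a composite estimand. But 2.1 classes rescue as non-response in so many words, names time to EASI 50/75/90 among the endpoints handled the same way, and no section states a hypothetical strategy.

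**The composite answer is already planned.** The binary EASI analyses treat rescue as failure, and 9.5.2 tabulates numbers achieving and censored. That limits the harm to the curve and the median. It does not reconcile them with the rest.

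**The median need not be borderline.** The 50% is an at-week-16 rate, the share by week 16 may be higher, and the curve continues afterwards. That is correct. The thresholds in step 4 show what can happen; they do not predict it.

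**Stronger readings that the documents do not support:**
- *The drug's effect is inflated.* The overstatement is per arm, and step 5 gives no fixed direction between arms.
- *Week-16 censoring in Part A is an error.* Ending follow-up at the switch is the SAP's convention elsewhere (9.5, 9.5.3.1) and leaves the curves to week 16 unchanged. Beyond week 16 the EASI 75/90 curves rest only on week-16 EASI-50 responders, which deserves a note. Any size would rest wholly on assumed rates.
- *Any Part B week-4 response after rescue in weeks 2-4 is counted.* It counts only if rescue has stopped before day 29, or if the visit falls before day 29 within its 3-day window. If rescue is still in use on day 29, EASI from that day is ignored.

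**Conclusion.** The point stands as an inconsistency within the SAP. Under the estimand in 2.1, the rescue censoring in 9.5.2 can only leave each arm's curve the same or higher and its median the same or earlier. For a true 50% by week 16 the excess is about 3-5 points with 10% rescued and 7-11 points with 20%. For a true 15% it is about 1 point with 10% rescued and 4-7 points with 40%. These sizes rest on assumed rescue rates, uniform rescue timing, the four response patterns, and no other censoring before week 16. The direction does not depend on the rates or the timing.

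The Part B paragraph is Part A text that does not fit: there is no switch, it is unclear whether a non-responder date exists, and the day-29 start does not match the Part B treatment rules.

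The analyses are descriptive, so the primary endpoints, power and type I error are unaffected. It should be fixed before the curves and medians are produced.

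**What to change.** 1. **SAP 9.5.2 and 9.5.3.1.** Keep rescued subjects in the risk set as not achieving to the end of the curve, or treat rescue as a competing event (Aalen-Johansen). State that a rescued subject is not censored later under the week-16 rule. Report cumulative incidence by visit, and give the median only where it is reached. If a hypothetical estimand is really intended for this endpoint, 2.1 must say so.
2. **SAP 9.5.3.1, Part B.** Delete the reference to switching and the week-16 non-responder censoring, and follow subjects to end of study.
3. **Part B rescue definition.** State which treatment, and from which day, counts as rescue for analysis, so that permitted background TCS is not counted as failure. Make 9.5.3.1, the day-29 rule in SAP 5.6, and protocol 7.1.5 and 7.1.7 agree. No change to any clinical rule is proposed.
4. **Part A after week 16.** Optional: show the EASI 75/90 curves to week 16 only, or add a note that later follow-up comes only from week-16 EASI-50 responders.

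Cost: SAP text and programming, with no new data. Some displayed response rates will be lower, and a median may be reported as not reached.
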